### Specific objectives

- To assess the efficacy of vitamin rich small fish, mola in improving vitamin A status (based on serum retinol concentrations, results from the Relative Dose Response (RDR) method, serum retinol binding protein and prealbumin concentrations). This will be done by comparing the increase in vitamin A status after supplementation of mola fish with the increase in vitamin A status after supplementation of non/low vitamin A rich big fish, rui and supplementation of rui with added retinyl palmitate, in a daily meal for 9 weeks to marginally vitamin A deficient children (3-7 y) in a Dhaka slum.
- To investigate the impact of intake of vitamin A rich small fish on iron status (based on haemoglobin, serum ferritin and serum transferrin receptor) in children in comparison with that of non/low vitamin A rich big fish and non/low vitamin A rich big fish with added retinyl palmitate.
- To investigate whether the factors: a) nutrient intake during study (based on repeated 24 h recall interview), b) initial vitamin A and iron status, c) changes in iron status, d) markers of infection (based on C-reactive protein (CRP) and  $\alpha$ -1 anti-chymotrypsin (ACT)), e) morbidity during study (based on incidence of infection such as diarrhoea, acute respiratory infections, fever, measles and night blindness), f) marker of protein energy malnutrition (based on prealbumin), g) initial and/or change in nutritional status (based on height, weight, MUAC) affect the change in vitamin A status after intake of vitamin A rich small fish in comparison with that of intake of non/low vitamin A rich big fish and non/low vitamin A rich big fish with added retinyl palmitate. In addition, if an effect is seen it will be investigated whether some subgroups benefit more than others from the intervention.
- To investigate qualitatively the mothers' perceptions of the effect of the mola supplementation on the general well being of the children as well as the acceptance of mola for habitual use among the children and their families.

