## Data Analysis

Describe plans for data analysis. Indicate whether data will be analyzed by the investigators themselves or by other professionals. Specify what statistical softwares packages will be used and if the study is blinded, when the code will be opened. For clinical trials, indicate if interim data analysis will be required to monitor further progress of the study. (TYPE WITHIN THE PROVIDED SPACE).

The first, second and third specific objectives refer to the results from the feeding trial (n=180, one test meal for 9 weeks). The fifth specific objective refers to the results for health, food intake, morbidity and nutritional status from the screening (pre-feeding trial) (n=550).

The data from the feeding trial is longitudinal as in each individual, each indicator is measured more than once over time. For indicators for changes in vitamin A and iron status, analysis of covariance will be used, testing group effect as a factor with nutrient intake during study, initial vitamin A and iron status, changes in iron status, markers of infection, morbidity during study, marker of protein energy malnutrition, initial and/or change in antropometry as covariates. Thus, comparisons of changes in the indicators between the three groups will be analysed (specific objectives one and two). In addition, the effect of the above mention variables on changes in the indicators for vitamin A and iron status will be explored. If an effect is found, sub group analysis will be performed (specific objective three).

In order to study the relationship between the indicators for vitamin A and iron status, parasites, infection, morbidity, food and nutrients intake and anthropometry, (multi)-analysis of variance will be used (specific objective five).

Variance homogeneity of residual variation will be investigated through plots of standardised residuals against predicted values. Normal distribution of data will be investigated graphically and by Wilk-Shapiro's test for normal distribution. If variance homogeneity does not exist or the data are not normally distributed, suitable mathematical transformations will be tried before nonparametric statistical analysis is performed.

The effect of sample size on the results obtained will be explored.

The children (n=550) are given a unique number at *screening*, numbers 300-850.

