## **5. Evaluation**

The proposed evaluation component is adequate.

The research includes collection of information on many potential confounding factors. If properly analyzed, this information will be invaluable to understand the mechanisms by which the intervention affected the outcomes, and also to document whether some subgroups benefited more than others from the intervention. For this latter purpose, however, the authors will need to test the statistical significance of two-way interactions between treatment groups and the characteristics of interest. These types of analyses should be added to the analytical plan.

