### **3.4 Evaluation**

*3.4.1 Reviewer's comment:*

The research includes collection of information on many potential confounding factors. If properly analyzed, this information will be invaluable to understand the mechanisms by which the intervention affected the outcomes, and also to document whether some subgroups benefited more than others from the intervention. For this latter purpose, however, the authors will need to test the statistical significance of two-way interactions between treatment groups and the characteristics of interest. These types of analyses should be added to the analytical plan.

*Response:*

The results for parasites, infection, morbidity, food intake and anthropometry can be used as covariates in objectives 1 and 2 for the three groups of children (n=180 in total).

For indicators for changes in vitamin A and iron status, analysis of covariance will be used, testing group effect as a factor with parasites, infection, morbidity, food intake and anthropometry as covariates. Thus, comparisons of changes in the indicators between the three groups will be analysed. In addition, the effect of parasites, infection, morbidity, food intake and anthropometry on changes in the indicators for vitamin A and iron status will be explored. If an effect is found, sub group analysis will be performed.

We acknowledge that we need expert advice from a qualified statistician. We will be assisted by a statistician from The Royal Veterinary and Agricultural University, Denmark, during the statistical analysis of data. He has been involved in the planning of the study design, and the details of the analysis are being developed as the study plan and implementation progress.

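### Subgroup analysis is triggered by a covariate's effect on the outcome, not by a group-by-covariate interaction, so the stated rule does not address which children benefit more

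*Protocol*

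**What the plan says.** Protocol, Data Analysis: change in the vitamin A and iron indicators is analysed by analysis of covariance, with group as factor. The covariates include "nutrient intake during study, initial vitamin A and iron status, changes in iron status, markers of infection, morbidity during study", a marker of protein energy malnutrition, and "initial and/or change in antropometry as covariates". The section adds that "the effect of the above mention variables on changes in the indicators for vitamin A and iron status will be explored", and the next sentence is the trigger: "If an effect is found, sub group analysis will be performed (specific objective three"). No product term between group and any covariate is named.

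Protocol, Specific objectives, third objective: seven lettered factors (a to g) are to be examined for their influence on the change in vitamin A status after mola compared with the two rui diets. It closes: "if an effect is seen it will be investigated whether some subgroups benefit more than others from the intervention".

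Appendix 11 (third referee for the funder, second round, section 5, Evaluation): to find out who benefits more, "the authors will need to test the statistical significance of two-way interactions between treatment groups and the characteristics of interest". The referee asked for this to be added to the analysis plan. The investigators' reply (Appendix 12, section 3.4) says that "the effect of parasites, infection, morbidity, food intake and anthropometry on changes in the indicators for vitamin A and iron status will be explored" and that subgroup analysis follows if an effect is found. It adds no interaction test.

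**The concern.** A covariate can be related to the outcome without altering the treatment effect. Infection may lower serum retinol equally in all three groups; that makes it prognostic and says nothing about whether mola works better in uninfected children. Conversely, a factor can alter the treatment effect while its average relation to the outcome is close to nil. A main effect is therefore neither necessary nor sufficient for the question in objective three.

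The covariate list also mixes baseline variables with variables measured during or after feeding: intake during the study, morbidity during the study, change in iron status, and change in anthropometry. The diets may shift these, and the second objective treats iron status as an outcome of the diets. Children grouped by such variables are no longer compared as randomised.

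At stake is the trial's statement on who gains from mola, which could influence whom later food programmes target.

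**Working it through.** **Inputs** (Protocol, Calculation of sample size): difference in change d = 0.15 µmol/L, SD 0.20 in each group, two-sided α = 0.05, power 0.90, 37 per group, 60 after allowing for 40% dropout.

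**The plan's own figure.** (1.96 + 1.28)² × (0.20² + 0.20²) / 0.15² = 10.50 × 0.08 / 0.0225 = 37.3; the protocol states 37. 37 / (1 − 0.40) = 61.7; the protocol states approximately 60. Both reproduce, and neither is in dispute.

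**Separate tests when nothing differs.** Assume two equal halves, the same true effect of 0.15 in both, and one test per half for mola against one control.

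- 37 per arm (18.5 per half): SE = 0.20 × √(2/18.5) = 0.0658. Power p = Φ(0.15/0.0658 − 1.96) = Φ(0.32) = 0.626. Exactly one half significant: 2p(1 − p) = 0.468.
- 60 per arm (30 per half): SE = 0.20 × √(2/30) = 0.0516. p = Φ(0.945) = 0.828, and 2p(1 − p) = 0.285.

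The same calculation over other uniform effects:

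| True effect (µmol/L) | 37 per arm | 60 per arm |
|---|---|---|
| 0.07 | 30% | 40% |
| 0.10 | 44% | 50% |
| 0.12 | 49% | 46% |
| 0.15 | 47% | 29% |
| 0.20 | 24% | 5% |

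**With the trigger included.** This was simulated with two arms, 4,000 runs per case and a uniform effect of 0.15. The covariate was purely prognostic, with an assumed correlation of 0.3 to 0.5 with change. The trigger fired in 74–100% of trials. Trigger plus discordant halves occurred in 35–44% at 37 per arm and 22–25% at 60 per arm. A group-by-covariate interaction test was significant in 5.0–5.6%. If the covariate is unrelated to change, trigger plus discordance occurs in only 1–2%.

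**Missed effect modification.** Let the effect truly differ by 0.30 between halves.

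- If the covariate's average effect over the two arms is zero, the trigger fires in about 4% of trials, while an interaction test finds the difference in 88–98%.
- If the covariate acts in the treated arm only, the trigger fires more often (65% at 37 per arm, 85% at 60), still below the interaction test (89% and 98%).

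**Splits on a variable shifted by the diet.** At 60 per arm, with an assumed correlation of 0.5 with the outcome, a shift of 0.5 SD moves the within-subgroup effect from 0.15 to about 0.12, and a shift of 1 SD to about 0.09. Both subgroups move about equally.

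**Power of the right test.** The SE of the difference between halves is √2 times the half-sample SE. For a true difference of 0.15: Φ(0.15/0.0930 − 1.96) = 0.36 at 37 per arm, and Φ(0.15/0.0730 − 1.96) = 0.54 at 60 per arm.

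**The case against.** The protocol says only that subgroup analysis will be done. It mentions neither median splits nor separate tests, and a statistical analysis plan could settle the method; the protocol says that details are still being developed with a statistician. This stands as a limit on the percentages, which are conditional on separate testing. It does not rescue the trigger, which is a stated decision rule and not a detail left open.

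The word effect could be read more kindly. Objective three speaks of factors affecting the change after mola in comparison with the other diets, which comes close to effect modification, and its last sentence could refer to an intervention effect. But Data Analysis ties the trigger to the covariates' effect on change, and an intervention effect is not an interaction test either.

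The reply in Appendix 12 concerns an earlier design, in which objective three was the screening analysis. The present objective three does take up the referee's question about who benefits. Even so, the current Data Analysis section keeps the covariate-effect trigger and adds no interaction.

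The 47% belongs to the maximum dropout of 40%. The Compliance section cites nearly 90% follow-up in previous studies and expects at least 80% attendance. If these are taken as retention, 48 to 54 per arm give 39–34% by the same formula.

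A reader might infer that a false contrast is nearly certain over all the factors. The documents do not support that: the splits are of the same children and so not independent, and only prognostic factors reliably trigger. A reader might also infer that the protocol prescribes splits on post-randomisation variables. It lists them as covariates; such splits follow only because the trigger refers back to the whole list.

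**Conclusion.** The point holds as a wrongly stated rule. The trigger tests whether a covariate predicts change, objective three asks whether the covariate alters the benefit of mola, and no interaction test appears in the plan although one was requested.

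If subgroup benefit is read from separate tests in equal halves, the chance of a spurious contrast for one factor at the design values is about 47% at 37 per arm or 29% at 60 per arm. It is about 22–44% once the trigger is simulated for a prognostic covariate, against about 5% per interaction test. These rates depend on the true effect and can fall to 5% (0.20 at 60 per arm). No figure for the whole family of factors is claimed.

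Subgrouping on variables measured after randomisation is a separate fault. In the model used, it biases the effect within subgroups; it does not by itself create a difference between them.

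A reader might infer that the trial's main result is compromised. It is not: the primary retinol comparison, the sample size and objectives one and two do not depend on this rule. The change should be made, because the conclusion of objective three rests on it.

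**What to change.** Replace the trigger sentence in Data Analysis with text such as: effect modification will be examined by group × baseline-covariate interaction terms in the analysis of covariance for a short pre-specified list, namely screening retinol, screening iron status, screening CRP/ACT, initial anthropometry, age and sex. Subgroup estimates with confidence intervals will be given only beside the interaction p-value and labelled exploratory.

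State two limits. Power is about 36–54% for a 0.15 difference in effect between halves, so a non-significant interaction does not show that the effect is uniform. And the tests are unadjusted: six independent tests carry a 1 − 0.95⁶ = 26% chance of at least one false positive, and more if several iron indicators are tested.

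Make no claim of subgroup benefit on variables measured during or after feeding. Reword items a, c and e and the change part of item g of objective three as descriptive associations, and state that infection markers used for effect modification are the screening values.

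The cost is one paragraph in Data Analysis and a small edit to objective three. No new data or additional children are needed.

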**5 b) If information is to be withheld from a subject, justify this course of action?**

There is hardly any information to be withheld. However, the subjects will be explained that they are randomized to receive one of the three types of blended fish, *mola*, *ru* and *ru with added vitamin A* dishes.

They will be informed that two of the fish dishes will contain vitamin A and one fish dish will contain Low/ no vitamin A. However neither the subjects/ mothers nor the study staff will know which type of fish dish they are going to receive during the feeding trial. This is done in order to eliminate bias.

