### Test meals

A pilot study was conducted in the Mirpur slum in October 2000 to develop and test the recipes to be used in the study as well as the procedures and the logistics, in terms of physical set up and manpower of carrying out the study. The dishes developed were cooked and served to 20 children for 5 days. Based on their feedback, adjustments were made. Samples of raw mola and rui and the corresponding cooked fish curries were taken to determine cooking loss of vitamin A. Samples of the cooked vegetable curries were also taken for determination of vitamin A.

The test meals in the different intervention groups have been designed in such a way that they appear and taste as similar as possible. The test meals will consist of rice, a fish curry and a vegetable curry. All foods given in the test meals other than mola are non/low vitamin A rich foods. Rice will be given *ad libitum* in order to adjust for the differences in energy needs due to different ages. Subsequently, all children are given the same fixed amount of rice, the few children who ask for more will be given more. The fish curry to be used in the intervention groups will differ only with respect to the fish species either small fish, mola or big fish, rui. The other ingredients of the fish curry will be onion, garlic, ginger, turmeric, chilli seed, iodised salt and soybean oil. The amount of cooked fish curry used in the intervention groups is fixed to correspond to either 45 g raw cleaned mola or rui/child/meal. The cooked mola curry will be homogenised (blended) so that the vitamin A in mola is uniformly distributed throughout the whole amount. The rui curry will also be homogenised. It was observed that the two fish curries differed in colour, the mola curry being dark green and the rui curry had a yellow tinge. The same vegetable curry will be used in all intervention groups during the study and will be served in a fixed amount. The vegetable curry will consist of bottle gourd in addition to potato, cucumber, onion, mug dal, garlic, ginger, turmeric, chilli seeds, iodised salt and soybean oil.

The recipe for 200 children are shown in appendix 14. However, we shall offer cooked rice 400g, vegetables 200g and blended fish (mola/rui) curry 90 g.

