In the positive intervention group, retinyl palmitate solution will be added to the meal of each child at serving. In order to ensure that the vitamin A recommended intake is met in the vitamin A rich and positive control groups, the daily test meal will contain approximately 500 RE/d.

Mola (300 kg) and rui (1100 kg) will be caught over a period of 4-6 months (starting at the end of 2001 and completing in the beginning of 2002). The fish will be cleaned, packed, weighed in daily portions and stored frozen at the Mymensingh Aquaculture Extension Project until transport to Mirpur. The rice (2400 kg) will be purchased from the Bangladesh Rice Research Institute. The vegetables (6500 kg) will be supplied by a local wholesale vendor.

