For the nutrient analyses of dishes, duplicate samples will be collected in labelled plastic boxes and stored frozen. One sample each of cooked rice (n=5) and vegetable curry (n=5) will be taken biweekly. For the three fish dishes, one sample each will be taken every week (n=9), in total 27. The duplicate samples will be used for chemical analyses of dry matter, vitamin A, energy, protein, fat, iron, calcium and zinc.

In order to motivate the children to comply with the study procedure, each child will be given a notebook, a pen and an identification card that can be hung around his/her neck. The identification card will be colour coded (each intervention group having a different colour) and include the child's name, ID number, parents' names, camp name, dates of study and the child's picture.

The research assistants will record all data collected daily with respect to attendance of the children, leftover dishes and duplicate samples and enter them in a computer programme.

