Children (n=180) who are selected for participating in the feeding trial are randomly assigned to the 3 treatment groups and subsequently given another number; group 1: 001-060, group 2: 061-120 and group 3: 121-180. If more than one measurement is done on the same child of a parameter, the child will be labelled with the above given number followed by another number starting with 1, i.e. **child number - 1**, **child number- 2** .. etc.

The blood analysis will be done without knowledge, of which group the children are assigned, since every blood analysis is given a unique number. The data analysis will be done without knowledge of which intervention group the children are assigned. The groups will be decoded at the completion of the analysis.

The co-principal investigator Ph.D. scholar [name] will do the major statistical analysis. During the statistical analysis of data, a qualified statistician from The Royal Veterinary and Agricultural University, Denmark will give appropriate assistance. A statistician has been involved in the planning of the study design, and the details of the statistical analysis are being developed as the study plan and implementation progress.

The statistical analysis will be performed with the Statistical Analysis System software (SAS Institute, Inc., Cary, NC, USA).

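### Study numbers issued in blocks by arm undermine the laboratory and analyst blinding stated for data after allocation, and the statement that mothers and staff will not know the dish does not fit the design

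*Protocol*

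**What the plan says.** The Data Analysis section gives children two numbers. At screening, each of the 550 gets one in the range 300-850. The 180 who are enrolled are randomised and "subsequently given another number; group 1: 001-060, group 2: 061-120 and group 3: 121-180". Where a parameter is measured more than once, "the child will be labelled with the above given number followed by another number starting with 1".

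The same section then states the blinding. "The blood analysis will be done without knowledge, of which group the children are assigned", and the reason given is "since every blood analysis is given a unique number". The statistical analysis is also to be blind to group, with decoding when it is complete.

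A Study ID field stands on the 24 h recall form, the morbidity form and the perception of mola form. Food containers carry the child's identification number (Test meal preparation and distribution); which number is meant is not stated.

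On families and field staff, item 5b of the abstract summary for the ethics committee (the file holds two copies) says that neither subjects and mothers "nor the study staff will know which type of fish dish they are going to receive during the feeding trial". Against this, the Test meals section reports "the mola curry being dark green and the rui curry had a yellow tinge" and, for the positive control, "retinyl palmitate solution will be added to the meal of each child at serving". The section on meal preparation and distribution adds: "The identification card will be colour coded (each intervention group having a different colour". It also gives the three groups three floors and has kitchen helpers arrange the children by group.

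**The concern.** A number that encodes the arm carries the allocation onto every form and tube that bears it. Masking matters here because the plan leaves several choices open until the data are seen. These are transformation or a nonparametric method, the use made of a long list of covariates, subgroup analyses if an effect is found (all in Data Analysis), and a possible stratified analysis by meals eaten (Compliance). An analyst who can read the arm from the child's number makes those choices unmasked. At the bench, the same holds for decisions to repeat or reject an assay.

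A second stake is the reported data. Diet recall and morbidity come from household interviews by staff described as blind, and both are covariates in the analysis of covariance of change in vitamin A status. Reports coloured by knowledge of the arm would enter the adjusted comparison.

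**Working it through.** The check is mainly one passage set against another.

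1. **What a number reveals.** With numbers unrelated to arm, learning one child's dish unmasks one child; for any other child a guess is right 1 time in 3. With blocks, it unmasks 180 / 3 = 60 children. Once two blocks are identified, the third follows by elimination, so two observations unmask all 180. The block alone shows only who shares an arm; one link to a dish is needed to name it.

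2. **Where that link comes from.** Mola curry is recognisable by colour. The perception form is for the mola group only, says so in its introduction, and bears the Study ID, so a handful of these forms identifies the mola block. The Design section lists the arms 1 to 3, but nothing says that this order is the key to groups 1 to 3.

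3. **Who holds it.** The Key Personnel table gives the co-principal investigator the daily running of the project and the data analyses; Data Analysis confirms the main statistical role. The same table gives the principal investigator both overall supervision and the blood analyses.

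4. **Which samples are exposed.**
   - Screening bloods, which supply the baseline values, are numbered 300-850, and the Time schedule has their retinol assayed before randomisation. Not exposed.
   - Baseline bloods for the relative dose response test (3 x 15 = 45 children), drawn after randomisation. Exposed if labelled by the stated rule.
   - Endpoint bloods (180 children). Exposed on the same condition. Change is endpoint minus screening, so any error in the endpoint value passes into the change in full.

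5. **Does the unique number protect the laboratory?** The only construction rule in the section is child number plus suffix, and such a label is itself unique. Uniqueness holds whether or not there is a separate laboratory code; independence from arm holds only if there is one. The text does not settle which.

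6. **Mothers and field staff.** Item 5b says that they will not know the dish. The curries differ in colour, each group has its own floor, cards are coloured by group, and in the positive control the vitamin is added at serving. Staff who serve the meals cannot be unaware of mola versus rui.

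7. **Effect on the trial's numbers.** The sample size reproduces: (1.96 + 1.28)^2 x (0.20^2 + 0.20^2) / 0.15^2 = 10.4976 x 0.08 / 0.0225 = 37.3, against 37 stated; 37 / 0.6 = 61.7, against about 60. The numbering does not alter it.

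8. **Assay runs, for scale only.** The protocol gives no assay order, run count or between-run variation. Suppose, purely as an assumption, that endpoint sera were run in number order so that arms fell in different runs, with an uncorrected shift of 2.5, 5 or 10% of 0.70 umol/L. That is 0.0175, 0.035 or 0.07 umol/L, or 12, 23 or 47% of the planned difference of 0.15. With SE = 0.20 x sqrt(2/n), that is 0.0365 for n = 60 and 0.0465 for n = 37, a nominal 5% test would reject falsely in 7.7, 16 or 48% of trials (n = 60), or 6.6, 12 or 32% (n = 37). The spread shows that no single figure can be attached to this protocol.

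**The case against.** Three stronger readings are tempting, and the documents support none of them.

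- **That laboratory and analyst blinding is impossible.** The unique number on each blood analysis may be a separate laboratory code, in which case the laboratory is blind. The analysis of covariance needs a group code anyway, and codes 1, 2 and 3 can stay masked until decoding. This stands. What remains is that the text does not secure the laboratory code, and that the analyst works daily where the dishes are served.
- **That the arm can be read from any label.** Screening samples carry arm-free numbers, and a block names an arm only once it is linked to a dish. This stands and limits the point to material collected after allocation.
- **That the type I error is inflated.** This would need an assay order, a run count and a between-run variation that the protocol does not give. The section on biochemical markers of infection also cites extensive internal and external quality control. Run allocation commonly belongs in a laboratory procedure, so its absence is not an error. A run shift falling between arms is a possibility to guard against, not a result.

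It can also be said that most of what mothers and staff know comes from the serving room, which renumbering would not change. That is right, and it is why the ethics statement is a separate matter. The primary outcome, serum retinol by HPLC, is less open to reporting bias than recall or morbidity. Colour cards and separate floors have a use: a second-round comment to the funder warned of children being mixed up between groups. That is a fair reason to keep them. It is not a reason to describe the field staff as blind, particularly as a first-round comment had already said that assignment probably could not be blinded and had pressed for a blind data analysis.

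**Conclusion.** The concern holds within limits. Arm-blocked numbers, used as the label for repeat measurements and, on a natural reading, as the Study ID on three forms, turn knowledge of one child's dish into knowledge of 60 children, and of two into all 180. This undermines the laboratory and analyst blinding stated in Data Analysis for post-allocation samples and records. It does not touch screening samples and does not rule blinding out. The conclusion assumes that Study ID means the 001-180 number (the forms show the mapping number separately) and that no independent laboratory code is in use, since none is described.

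Separately, item 5b is not true as designed: mola versus rui is recognisable, and field staff can tell the groups apart. The bias in the retinol comparison cannot be sized from the protocol, and the sample size is unaffected. This merits correction because the remedy is nearly free before numbers are issued.

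**What to change.** - Issue 001-180 in an order unrelated to arm. Hold the list linking number to arm away from the laboratory and the analyst.
- State that tubes drawn after allocation carry a laboratory code independent of the child's number, and spread the three arms over assay runs.
- Give the analyst masked group codes until decoding, and keep the mola-only perception forms out of the analysis file until then. Because the analyst also runs the field work, the outcome file should not carry the field number.
- Correct item 5b in both copies of the ethics summary: mola versus rui can be recognised, and field staff are not blind. Claim blinding for the laboratory and the analyst only.

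The cost is a renumbered list, one set of laboratory labels, someone to hold the key, and a wording change for the ethics committee. Neutral card colours, or adding vehicle to the other plates at serving, are optional; coloured cards may guard against serving the wrong dish, and that should be weighed before they are dropped.
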